## 1 PROTOCOL SUMMARY

### 1.1 SYNOPSIS

**Title:**

A Brief Intervention to Improve Stroke Preparedness

**Grant Number:**

U01MD010579

**Study Description:**

This is a randomized controlled behavioral intervention trial to assess the efficacy of a brief intervention to increase stroke preparedness.

**Objectives:**

To test the efficacy of a brief intervention to increase stroke preparedness (recognition of stroke and the importance of calling 911).

**Endpoints:**

Primary Endpoint:

- Behavioral intent to call 911 using a self-administered survey

Exploratory Endpoints:

- Stroke symptom recognition
- Stroke self-efficacy, attitude, social norms

**Study Population:**

Adults in the Flint Community

**Description of Study Intervention/Experimental Manipulation:**

Randomized control study to assess the efficacy of a stroke preparedness intervention. Subjects will be randomized to a brief face-to-face stroke preparedness intervention compared to a healthy lifestyle stroke risk reduction intervention.

**Study Duration:**

About 30 minutes

**Participant Duration:**

Single-session

### 2.1 STUDY RATIONALE

With nearly 800,000 strokes in the US annually, stroke is a leading cause of disability. The number of US stroke survivors is projected to increase from 7 to 10 million by 2030 given the aging baby boomer generation and declining stroke mortality. Because most people survive their stroke, disability is the greatest challenge facing survivors and their families. About two-thirds of stroke survivors are left with disability. Acute stroke treatments reduce disability but

are underutilized particularly in African Americans. Acute stroke treatments will reduce the relative risk of post-stroke disability by over 30%.

**Specific Aim 1:** To assess whether a scientific theory-driven, face-to-face brief behavioral intervention increases behavioral intent to call 911 among adults in Flint, MI.

**Specific Aim 2:** To assess whether a scientific theory-driven, face-to-face brief behavioral intervention increases stroke recognition and stroke self-efficacy among adults in Flint, MI.

## 2.2 BACKGROUND

Post-stroke disability is common, costly and projected to increase. Most of the more than 7 million stroke survivors in the US have disability. Acute stroke treatments, which include intravenous tissue plasminogen activator (tPA) and intra-arterial treatment, substantially reduce post-stroke disability but are administered to less than 5% of stroke patients. These treatments are particularly underutilized in Flint, Michigan, where the rate of acute stroke treatment is half the national rate. In fact, Flint has the lowest treatment rate of any region of its size in the entire US, which only exacerbates the existing health disparities in this predominantly African-American community. The low treatment rates of the Flint community are illustrative of racial disparities in stroke — African Americans have a higher incidence of stroke, receive acute stroke treatments less often and experience greater post-stroke disability than non-Hispanic whites. These inequities can be at least partially addressed with interventions to increase acute stroke treatment rates; but practical, cost efficient and sustainable interventions are lacking.

## 2.3 RISK/BENEFIT ASSESSMENT

### 2.3.1 KNOWN POTENTIAL RISKS

The Stroke Ready workshop is community-based education with no more than minimal risk.

Physical risks: We do not anticipate our intervention will induce physical risks as it is all based on educational materials.

Psychological risks: We do not anticipate our intervention will induce psychological risks as we provide positive messages.

Financial risks: We do not anticipate any financial burden all Stroke Ready education and activities are free to the public.

Legal risk: We do not anticipate that our research protocol will include any additional legal risks.

### 2.3.2 KNOWN POTENTIAL BENEFITS

The goal of this project is to provide stroke preparedness education to increase acute stroke treatment rates. Participants will uniformly gain access to stroke knowledge and education. It is hoped that by increasing knowledge of stroke symptoms, stroke treatments and the importance of calling 911, subjects will be more likely to recognize a stroke and call 911 should they see it

occur in their community. This will decrease time to hospital arrival and allow us to better care for stroke patients.

### 2.3.3 ASSESSMENT OF POTENTIAL RISKS AND BENEFITS

All members of the research team have been trained in research ethics, confidentiality protection, and HIPAA prior to and throughout the study period through the Program for the Education and Evaluation in Responsible Research and Scholarship (PEERRS) training program at the University of Michigan Medical School. Any additional research personnel must also pass PEERRS certifications.

## 3 OBJECTIVES AND ENDPOINTS

Table 1: Stroke Preparedness Brief Intervention Outcomes		
Primary Outcome		
Intervention Goal	Outcome Measure	Timing
Increase behavioral intent to call 911	STAT	Pre-post
Secondary Outcome		
Increase stroke recognition	Survey	Pre-post
Improve self-efficacy, attitude, social norms	Self-efficacy, Attitude, subjective norm	Pre-post
Satisfaction		Post

## 4 STUDY DESIGN

### 4.1 OVERALL DESIGN

This is a randomized controlled trial of a stroke preparedness intervention to increase behavioral intent to call 911 (Figure 1). The control group will receive a healthy lifestyle stroke risk reduction intervention. The intervention was designed as part of HUM00126955.

[figure not shown]

Figure 1: Trial Design

### Brief Intervention

Peer leaders will deliver the brief stroke preparedness intervention.

These core components include, and are defined as follows:

1. **What is Stroke:** defines what a stroke is and what causes it.
2. **Stroke Happens :** facts about incidence and prevalence of stroke, as well as defining the consequences of stroke.
3. **Stroke Signs (FAST):** Review of signs of stroke—face drooping, arm weakness, speech difficulties, and time to call 911, as well as how to check for each sign.
4. **Stroke is treatable. TPA—the clot blaster:** visual demonstration and/or illustration showing what happens during a stroke and how TPA works to remove a blockage in the brain.
5. **Time is everything:** explanation that medicine to treat stroke can only be given in the hospital, and that earlier treatment is given, the better the chance of recovery.
6. **Stroke Ready Action Plan:** a step-by-step plan to guide a person through calling 911 if they see signs of stroke, and a reminder of the steps to follow when doing so.

The healthy behavior intervention consists of patient materials from the American Heart Association.

The intervention will be conducted by members of the research team in space provided by the community clinics and senior center, similar to our previous procedures (HUM00084543, HUM00145724). The interaction (pre-test—intervention—post-test) will take about 30 minutes. We will provide the subjects \$20 in cash in appreciation of their time. Identifiers will not be collected and thus we will not collect identifiers of subjects who are paid for their participation.

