### 4.2 SCIENTIFIC RATIONALE FOR STUDY DESIGN

We selected a randomized controlled trial design to account for temporal trends, test-retest bias and participant selection. The Stroke prevention group will be offered the opportunity to completed the stroke preparedness intervention if they chose.

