## 5 STUDY POPULATION

### 5.1 INCLUSION CRITERIA

Adults over the age of 18 years.

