### 5.3 STRATEGIES FOR RECRUITMENT AND RETENTION

Subjects will be recruited from Hamilton Community Health Center and Senior Centers. We have recruited from both of these venues in the past (HUM00093846, HUM00145724). The subjects will be invited to participate when asked by a team member or member of the clinic medical staff. Subjects from the senior center will be recruited during center events. Recruitment announcements, flyers, internet platforms, and word-of-mouth may also be used.

There is no retention. Subject identifiers are not collected and subjects are not contacted after initial interaction.

Subject agreement will be sought at the start of the interaction by members of the research team. Any subject who declines will be thanked for their participation and the interaction will cease. A copy of the agreement form will be provided to subjects.

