### STATISTICAL CONSIDERATIONS

### 6.2 STATISTICAL HYPOTHESES

#### 6.2.1 ANALYSIS OF ENDPOINT(S)

The primary analysis will fit a linear regression model with the outcome of change in behavioral intent to call 911 (post minus pre) and main effect-coded binary predictor intervention group. Results will be reported as parameter estimates, 95% confidence intervals, or as the average

marginal effects and 2-sided p-values. We anticipate the tertiary/exploratory variables will be analyzed using the same strategy, although logistic regression models may be used depending on the properties of the collected data.

Previous studies note a 6 point improvement (sd=6) in behavioral intent to call 911 based on (21 stroke vignettes) after a 15 minute video intervention. There was no control group and thus we cannot assess the test and re-test properties of their measure. Given our measurement instrument is fewer questions and has higher baseline estimates than the previously used estimate, STAT, that the sample size calculations are based off of, we anticipate less improvement. We estimate a 3 point improvement in the intervention group and a 2 point improvement in the control group (test-re-test). Thus with sd (2), power 80, alpha 0.05, we plan to enroll 63 subjects in each arm.

The table below is intended to capture changes of IRB-approved versions of the protocol, including a description of the change and rationale. A **Summary of Changes** table for the current amendment is located in the **Protocol Title Page**.

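### Does anonymous, cash-paid enrolment with no rule against repeat participation put the primary comparison at risk?

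*Combined protocol and SAP*

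**What the plan says.** The synopsis gives the participant duration as "Single-session". Section 5.3 says that "Subject identifiers are not collected and subjects are not contacted after initial interaction", and Section 6.2.1 sets the sample size in people: "we plan to enroll 63 subjects in each arm". The intention is one enrolment per person.

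The eligibility text is short. Section 5.1 has one criterion, "Adults over the age of 18 years", and Section 5.2 lists no exclusions. On payment, the Brief Intervention part of Section 4.1 says "Identifiers will not be collected and thus we will not collect identifiers of subjects who are paid for their participation"; the $20 in cash goes to subjects for their time.

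Section 5.3 names a community health center and senior centers as the recruitment sites. People are invited by a team member or clinic staff, or at center events. It then adds: "Recruitment announcements, flyers, internet platforms, and word-of-mouth may also be used".

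Section 4.2 says of the control arm: "The Stroke prevention group will be offered the opportunity to completed the stroke preparedness intervention if they chose". The primary model in Section 6.2.1 is a linear regression of the change score on a "main effect-coded binary predictor intervention group", with one record per participant.

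**The concern.** Several features together seem to invite repeat enrolment. Cash is paid for about 30 minutes, payment leaves no trace of who received it, and recruitment may be open. The venues are also places that people visit more than once. A returning person would meet the written criteria. The survey asks for gender, age, race, ethnicity, schooling and stroke experience, so matching answers could raise a suspicion but could not settle it.

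A repeat visit could matter in two ways. First, the regression would treat two records from one person as two independent people, which could distort the standard error and the type I error rate. Second, a returner has already seen the test and may already have had the preparedness content, either by assignment or through the offer made to controls. The second visit may then show little or no difference between arms, which would pull the estimated effect towards zero. The sample size has almost no reserve to absorb that loss.

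**Working it through.** **Inputs.** Section 6.2.1 gives expected improvements of 3 points (intervention) and 2 points (control), so the difference is δ = 3 − 2 = 1. It also gives SD = 2, power 80%, α = 0.05 and two-sided p-values. With 63 per arm there are 126 records. The share of repeat records, f, and the within-person correlation of change scores, ρ, are not in the documents. Both are assumptions.

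**The plan's own figure.** By the normal approximation, n per arm = 2(1.960 + 0.842)² × SD²/δ² = 2 × 7.85 × 4/1 = 62.8, which rounds up to 63. The stated sample size reproduces. The standard error of the difference is 2 × √(2/63) = 0.356, so the expected test statistic is 1/0.356 = 2.81. Power is 80.1% by the normal approximation and 79.5% by the t-test. The t-test value is the baseline below.

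**Dilution of the effect.** If repeat records show no difference between arms, the average difference becomes δ = 1 − f. If they show half the difference, it becomes δ = 1 − f/2. Power by the noncentral t distribution, 63 per arm, SD 2:

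| Assumed f | Repeat records of 126 (rounded) | Power, no effect in repeats | Power, half effect in repeats |
|---|---|---|---|
| 0 | 0 | 79.5% | 79.5% |
| 1% | 1 | 78.7% | 79.1% |
| 2% | 3 | 77.9% | 78.7% |
| 5% | 6 | 75.3% | 77.5% |
| 10% | 13 | 70.7% | 75.3% |

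At f = 2% the loss is 79.5 − 77.9 = 1.6 points in the worse case and 79.5 − 78.7 = 0.8 points in the milder one. A simulation of 100,000 trials per setting agrees. It used fresh randomization at each visit, ρ = 0.5 and repeat visits gaining 2 points in both arms. The mean differences were 0.99, 0.98, 0.95 and 0.90, and power was 78.6%, 77.3%, 75.5% and 70.0%, for 1, 3, 6 and 13 repeats.

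**Type I error.** The variance of the difference in means without repeats is 2 × SD²/63. Each repeated pair adds 2ρ × SD²/63² if both visits fall in the same arm, and subtracts the same amount if they fall in opposite arms. With fresh 1:1 randomization about half the pairs fall each way, so the terms cancel on average. The simulation with no true effect bears this out: at ρ = 0.5 the rejection rates were 5.0%, 5.2%, 5.1% and 5.1% for 1, 3, 6 and 13 repeats. At ρ = 0.8 they were 5.0%, 5.0%, 5.1% and 5.1%.

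**One-sided allocation of repeats.** If every one of k repeats fell in the same arm, the variance would be multiplied by 1 + 2kρ/126. For k = 3 and ρ = 0.5 that is 1 + 3/126 = 1.024, and the rejection rate is about 5.3% (5.4% simulated). For k = 13 it is 1 + 13/126 = 1.103, and about 6.2% (6.1% simulated). If all repeats fell in the opposite arm, the test would be conservative. The text shown does not describe the randomization method and gives no mechanism for either extreme.

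**The case for a change.** The strongest case for acting is that the remedy is cheap and can only work in advance. One exclusion line and one verbal question would fit the step where agreement is already sought, and anonymity would be kept. Without identifiers, a duplicate cannot be confirmed afterwards. The plan itself takes retest effects seriously: it expects a 2-point gain in controls from retesting alone. With 63 per arm only just reaching 80% power, even small losses take the trial below its target.

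Much of this is true. The eligibility text contains no prior-participation rule, and a duplicate could not be verified. Three things limit its weight.

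- **The absence is not fully established.** The survey text available begins at Section B, item 9, and the agreement form is not visible. A question about earlier participation would naturally sit in either place.
- **The incentive is weaker than it looks.** Payment goes to subjects, and the plan does not promise it for each visit. The named recruitment route is personal invitation at a few sites, with sessions run face-to-face by the research team. Flyers and internet platforms are optional additions. The offer of the preparedness session to controls is not a second enrolment.
- **The remedy is itself partial.** Asking people whether they have taken part before relies on self-report, and the motive to misreport is the same cash that raises the worry. A self-generated code can be mis-entered or match by chance.

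**Conclusion.** No change to the plan is needed. The gap is real in the text shown, but it is a detail of conduct. The plan already states one session per person, and staff can act on that without a further rule. A handful of repeats would leave the primary test valid and cost little. At an assumed 1% to 2% of records, the loss is at most 1.6 points of power, and false positives stay at about 5%. The error works against the intervention by diluting the difference, so it does not create a spurious benefit.

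This rests on three assumptions: repeats are rare, each visit is freshly randomized, and the planning values of a 1-point difference and SD 2 hold. Rarity is the one that matters most. At 10% repeats with no effect, power would be 70.7%, but nothing in the documents suggests a rate that high in 126 face-to-face sessions. Collecting no identifiers is a fair trade-off in a minimal-risk educational study, and a written exclusion resting on self-report would add little protection.

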### 4.2 SCIENTIFIC RATIONALE FOR STUDY DESIGN

We selected a randomized controlled trial design to account for temporal trends, test-retest bias and participant selection. The Stroke prevention group will be offered the opportunity to completed the stroke preparedness intervention if they chose.

## 5 STUDY POPULATION

### 5.1 INCLUSION CRITERIA

Adults over the age of 18 years.

### 5.2 EXCLUSION CRITERIA

None

### 5.3 STRATEGIES FOR RECRUITMENT AND RETENTION

Subjects will be recruited from Hamilton Community Health Center and Senior Centers. We have recruited from both of these venues in the past (HUM00093846, HUM00145724). The subjects will be invited to participate when asked by a team member or member of the clinic medical staff. Subjects from the senior center will be recruited during center events. Recruitment announcements, flyers, internet platforms, and word-of-mouth may also be used.

There is no retention. Subject identifiers are not collected and subjects are not contacted after initial interaction.

Subject agreement will be sought at the start of the interaction by members of the research team. Any subject who declines will be thanked for their participation and the interaction will cease. A copy of the agreement form will be provided to subjects.

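### Venue type is used neither to stratify randomization nor in the primary model: a cheap chance to gain precision, not a flaw in validity

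*Combined protocol and SAP*

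**What the plan says.** Section 5.3 names two kinds of venue: "Subjects will be recruited from Hamilton Community Health Center and Senior Centers". The routes in differ. In general a team member or the clinic's medical staff invite people, whereas "Subjects from the senior center will be recruited during center events". Section 5.3 also allows flyers, internet platforms and word of mouth. Under Brief Intervention (Section 4.1), sessions take place "in space provided by the community clinics and senior center".

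On allocation, the synopsis says "Subjects will be randomized to a brief face-to-face stroke preparedness intervention compared to a healthy lifestyle stroke risk reduction intervention". Sections 4.1 and 4.2 repeat that the design is randomized. No readable text gives a method, block size or stratification factor.

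Section 6.2.1 takes the change score (post-test minus pre-test) as the primary outcome and regresses it on a "main effect-coded binary predictor intervention group". It names no venue term, other covariate or sensitivity analysis by venue. The sample size rests on gains of 3 and 2 points in the two arms: "Thus with sd (2), power 80, alpha 0.05, we plan to enroll 63 subjects in each arm".

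Section 5.3 adds that no identifiers are collected and nobody is contacted after the session.

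**The concern.** Session venue should be known before a participant is randomized, yet the plan uses it neither to balance the arms nor to explain variation in the outcome. A change score cancels a stable difference in level between venues. It does not cancel a difference in mean gain. Such a difference is possible here: the plan expects a 2-point gain in the control arm from retesting alone, twice the 1-point difference under test, and retest behaviour need not be the same in a clinic as at a senior-center event.

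What is at stake is precision. The sample size has no margin, so any variance that could be explained cheaply is worth explaining. The opportunity is also prospective only: if venue is not noted at the session, the stated lack of identifiers and later contact would rule out any adjustment or sensitivity analysis by venue.

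**Working it through.** **Inputs from Section 6.2.1.** Difference 3 − 2 = 1 point; SD 2; two-sided alpha 0.05; power 80%; 63 per arm (126 in total).

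**Assumed inputs.** The documents give neither the share p recruited at senior centers nor the gap g in mean gain between venue types. I take p = 0.5 (and 0.3 as a check) and g = 0.5, 1.0 and 1.5 points. SD 2 is read as the total SD, including any venue component.

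**1. The plan's own figure.** n per arm = 2 × 2² × (1.960 + 0.842)² / 1² = 62.79, rounded up to 63. This reproduces the plan. Power at 63 per arm is 80.1% by the normal approximation and 79.5% by the noncentral t distribution (64 per arm would be needed for 80%). The noncentral t is used below.

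**2. Effect of adjusting for venue.** The between-venue variance is p(1 − p)g², so the adjusted SD is √(4 − p(1 − p)g²). The equivalent number of extra participants is 126/(1 − share removed) − 126. With p = 0.5:

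| Gap g | Venue variance | Share of 4 removed | Adjusted SD | Power at 63 per arm | Equivalent extra participants |
|---|---|---|---|---|---|
| 0 | 0 | 0% | 2.000 | 79.5% | 0 |
| 0.5 | 0.0625 | 1.6% | 1.984 | 80.1% | about 2 |
| 1.0 | 0.25 | 6.2% | 1.936 | 82.0% | about 8 |
| 1.5 | 0.5625 | 14.1% | 1.854 | 85.2% | about 21 |

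These powers use 123 residual degrees of freedom, after spending one of 124 on venue. They take the arms as balanced on venue, which stratification would secure. With p = 0.3 they are slightly lower: 80.0%, 81.6% and 84.3%.

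**3. The other reading of SD 2.** If 2 is the SD within a venue, the total SD is √(4 + p(1 − p)g²). With p = 0.5, unadjusted power is then 78.9%, 77.1% and 74.1% for the three gaps, and adjustment brings it back to about 79.5%.

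**4. Chance imbalance.** Under simple randomization, the SD of the between-arm difference in venue share is √(2 × 0.25/63) = 0.089. The 95% range is ±1.96 × 0.089, about ±17 percentage points. Multiplied by g, this gives 95% limits of ±0.09, ±0.17 and ±0.26 points for the part of the estimate due to venue mix.

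**5. Whether that part comes on top of the standard error.** It does not. The unadjusted squared standard error is 4 × 2/63 = 0.1270. At g = 1 it splits into a venue part, 0.25 × 2/63 = 0.0079, and a remainder, 3.75 × 2/63 = 0.1190, which sum to 0.1270. The ±0.17 is 1.96 × √0.0079, so it already lies inside the unadjusted standard error of 0.356 (95% interval about ±0.70). Adjustment lowers the standard error to √0.1190 = 0.345.

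**6. Validity of the planned test.** In 20,000 simulated trials per setting (p = 0.5), the unadjusted test rejected a true null in 5.4%, 4.9% and 5.0% of runs at gaps of 0, 1 and 2 points, with mean bias near 0.

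**The case against.** The strongest reply is that nothing here is wrong. An unadjusted comparison in an individually randomized trial is valid, and Section 4.2 relies on randomization to deal with participant selection, which is legitimate. Steps 5 and 6 bear this out, and the reply stands in full. A reader might infer that an uneven venue mix biases the result. It does not: chance imbalance is one component of ordinary sampling error that the standard error already contains. The ±0.09 to ±0.26 figures are 95% limits under assumed gaps, not maxima.

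Second, the size of the benefit is assumed. No text gives or suggests a venue gap in mean gain, and a gap of 1.5 points exceeds the whole planned effect. That stands, and it is why the benefit is shown as a range that starts at nothing.

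Third, some inferences go beyond the text. One might suppose that the venues differ in age, but no ages by venue are stated, and the survey asks each participant's age anyway. One might suppose that venue will go unrecorded, but the survey text available begins at item 9 and Figure 1 is not shown, so this is unproven; staff may well log the site. The absence of stratification is likewise established only for the readable text. Nor do the documents define a clean two-level factor: they mention several senior centers, clinics in the plural and other recruitment channels.

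Fourth, no allocation procedure is described at all, and venue stratification is one choice within that wider gap. That is true, but it does not make the improvement less worthwhile.

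**Conclusion.** The point holds as a low-priority, inexpensive improvement in precision. Participants come from two kinds of venue by different routes, the readable text states no stratification, and the primary model has only the group term. The planned comparison is unbiased with correct type I error, and 63 per arm follows from the plan's own inputs, so no larger sample is called for.

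The size rests on the assumed venue split, the assumed gaps and SD 2 as the total SD. On those terms adjustment is worth 0.6 points of power at a gap of 0.5 (80.1 − 79.5), 2.5 at 1.0 and 5.7 at 1.5, and nothing if venues do not differ in mean gain. Part of this may overlap with what adjustment for the pre-test score would deliver; the figures are not net of that.

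**What to change.** - **Data collection:** record the session venue on each form, if this is not already done. This matters most, because it cannot be made good later.
- **Section 4.1:** state 1:1 randomization in permuted blocks, stratified by venue type (clinic or senior center), and define how a person recruited through another channel is classed, for example by where the session is held.
- **Section 6.2.1:** add venue type as a fixed effect in the primary model, and use the same model for the other outcomes. The two changes belong together: stratifying without the model term would leave the venue variation in the estimated standard error.

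The cost is one form field, a separate allocation list for each venue type, a sentence or two of text, and one of 124 degrees of freedom. If venues do not differ, power stays at 79.5% to one decimal place.
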